5.15.10. Eye Examinations

All individual level data from eye examinations following protocol amendment 4.0 will be presented in a listing.

5.16. Pharmacokinetics

Plasma concentrations of tavapadon and CV-0000053 (metabolite) will be determined using a validated LC-MS/MS method. PK data listings will be presented for the FAS population. PK summary tables and mean figures will be presented using the PK analysis set.

5.16.1. Pharmacokinetic Data Analysis

Plasma concentrations of tavapadon and CV-0000053 (metabolite) will be summarized separately using descriptive statistics by visit. Plasma concentrations of tavapadon and CV-0000053 that are <LLOQ will be reported as 'BLQ' in the data listings. Plasma concentrations that are BLQ will be treated as 0 for calculation of descriptive statistics. The geometric mean, however, will be calculated by imputing BLQ values as $\frac{1}{2}$ LLOQ. If the calculated mean concentration is below the limit of quantitation, the mean will be reported as BLQ and the SD and CV% shall be reported as not determined (ND). Mean plasma concentrations (SD) of tavapadon and CV-0000053 will be also be plotted versus time based on nominal visit.

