
 To evaluate the PK of tavapadon in this population 	Plasma concentrations of tavapadon and its metabolite (if required) at baseline (Day 1) and at Weeks 5, 11, 14, 22, and 27

Abbreviations: AE = adverse event, C-SSRS = Columbia-Suicide Severity Rating Scale, ECG = electrocardiogram, EQ-5D-5L = EuroQol 5 Dimension 5 Level, ESS = Epworth Sleepiness Scale, L-Dopa = levodopa, MDS-UPDRS = Movement Disorder Society-Unified Parkinson's Disease Rating Scale, MHIs = medication handling irregularities, PD = Parkinson's disease, PDQ-39 = 39-Item Parkinson's Disease Rating Scale, PK = pharmacokinetic, QUIP-RS = Questionnaire for Impulsive-Compulsive Disorders in Parkinson's Disease-Rating Scale, TEAEs = treatment-emergent adverse events, VAS = visual analog scale.

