4 TRIAL DESIGN

4.1 Overall Design

This is a prospective, Phase 3, multicenter, multinational, randomized, double-blind, placebo-controlled, parallel-group, 27-week trial to evaluate the efficacy, safety, tolerability, and PK of tavapadon as adjunctive therapy to levodopa (L-Dopa) in male and female subjects aged 40 to 80 years who have a diagnosis of PD (consistent with the UK Parkinson's Disease Society Brain Bank diagnostic criteria); a modified Hoehn and Yahr score of 2, 2.5, or 3 in the “on” state; a minimum of 2½ hours of “off” time on 2 consecutive days; and a good response to L-Dopa in the judgment of the investigator. The trial will include a Screening Period (maximum of 4 weeks), a 27-week Treatment Period, and a 4-week Safety Follow-up Period (Figure 1). Each subject will participate in the trial for up to approximately 35 weeks.

4.1.1 *Screening/Baseline Period*

Subjects who provide written informed consent will be screened for eligibility during the Screening Period. During the Screening Period, subjects will be trained in the use of the home diary (Hauser diary), and subjects and investigators (or qualified designee) will independently complete concordance testing on the Hauser diary (full details and requirements for conduct and successful completion of concordance testing are provided in the appropriated protocol-specific manual). Subjects who successfully meet the concordance testing criteria will complete the Hauser diary on at least 2 consecutive days (24-hour periods) within the 7 days before the Baseline Visit.

Subjects whose diary shows a minimum of 2½ hours of “off” time on each of the 2 days and who continue to satisfy the trial eligibility criteria at the Baseline Visit will be randomized in a 1:1 ratio to receive:

- Tavapadon ranging from 5 to 15 mg QD
- Placebo QD

4.1.2 **Treatment Period**

The dose of tavapadon will be gradually titrated to 15 mg QD in all subjects over the first 14 weeks of the trial during the Dose Titration and Dose Adjustment Phases unless prevented by intolerance. A reduction in dose (from 15 mg QD to 10 mg QD or from 10 mg QD to 5 mg QD) will be allowed based on individual subject tolerability. Subjects who require a dose reduction may be rechallenged with the higher dose, at the discretion of the investigator, to address symptomatic needs.

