The titration schedule, as shown in [Table 4](#), will be used for all subjects who are randomized to receive tavapadon. Subjects will take 3 tablets of IMP, either all tavapadon tablets, all placebo tablets, or a combination of tavapadon and placebo tablets, throughout the trial to maintain the trial blind.

Table 4 Tavapadon and Placebo Dosing Schedule

Trial Day	Titration Step	Blinded Treatment Assignment
		Maintenance Phase^c
		Maximum tolerated tavapadon dose (5-15 mg) or placebo QD

Abbreviation: QD = once daily.

- a. No deviations in the titration schedule up through 5 mg QD [REDACTED] will be allowed.
- b. The dose will be adjusted over the range of 5 to 15 mg [REDACTED] based on individual subject tolerability.
- c. Subjects will receive the highest tolerated dose level that is achieved during the Dose Adjustment Phase. No adjustment in the tavapadon dose will be allowed during the Maintenance Phase.

No deviations in the titration schedule up through [REDACTED] (5 mg QD) will be allowed. Titration of tavapadon should be guided by absence of tolerability issues that are reported as AEs and that are of sufficient severity resulting in significant dysfunction or distress to the subject. Any questions regarding tolerability issues and titration should be directed to the medical monitor before adjustments are initiated. The dose of tavapadon will be gradually titrated to the [REDACTED] dose (15 mg QD) in all subjects, as shown [Table 4](#), unless prevented by intolerance.

Subjects who are unable to achieve or tolerate the [REDACTED] dose (15 mg QD) may receive the [REDACTED] dose (10 mg QD). Subjects who cannot achieve or tolerate the [REDACTED] dose (10 mg QD) may receive the [REDACTED] dose (5 mg QD). Subjects who cannot achieve or tolerate the [REDACTED] dose (5 mg QD) will be discontinued from the trial. Subjects who require a dose reduction may be rechallenged with a higher dose to address symptomatic needs after at least 7 days at the lower dose during the Dose Adjustment Phase.

Subjects will receive the highest tolerated dose level that is achieved during the Dose Adjustment Phase for the duration of the subsequent 13-week Maintenance Phase. Adjustments in the dose of tavapadon will not be allowed during the Maintenance Phase. Subjects who cannot tolerate their maintenance dose will be discontinued from the trial.

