The first dose of IMP will be taken at the trial site at the Baseline Visit; all other doses will be taken on an outpatient basis. Assessments will be conducted in the clinic at the end of Weeks 2, 5, 8, 11, 14, 18, 22, 26, and 27. Subjects will complete the Hauser diary on 2 consecutive days within the 7 days before each scheduled postbaseline clinic visit. Blood samples for PK will be collected after administration of the first dose on Day 1 (~1 hour after dosing) and at the Weeks 5, 11, 14, 22, and 27 clinic visits.

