9.4.3 Other Analyses

Plasma concentrations of tavapadon and its major metabolite (if required) will be summarized by dose, visit, and nominal time (if applicable). All PK exposure-response analyses will be described in a separate PK analysis plan that will be finalized before database lock.

Plasma concentrations will also be pooled with data from other trials in a population PK analysis to describe the time course of plasma concentrations of tavapadon and the influence of covariates (eg, body weight, age, sex, race, concomitant medications) on PK parameters. The results of population PK analysis and response-exposure analyses will be presented separately from the main clinical study report (CSR).

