1.1. Study Overview

This is a prospective, Phase 3, multicenter, multinational, randomized, double blind, placebo controlled, parallel group, 27 week trial to evaluate the efficacy, safety, tolerability, and pharmacokinetics (PK) of flexible doses of tavapadon (5 mg to 15 mg once daily [QD]) as adjunctive therapy to levodopa (L Dopa) in male and female subjects aged 40 to 80 years who have a diagnosis of PD (consistent with the UK Parkinson's Disease Society Brain Bank diagnostic criteria); a modified Hoehn and Yahr score of 2, 2.5, or 3 in the "on" state; a minimum of 2½ hours of "off" time on 2 consecutive days; and a good response to L Dopa in the judgment of the investigator. The trial will include a Screening Period (maximum of 4 weeks), a 27 week Treatment Period, and a 4 week Safety Follow up Period. Details of schedule of assessments are provided in [Section 9.2](#).

A total of 368 subjects are planned to be randomized in a 1:1 ratio to receive tavapadon or placebo once daily (184 subjects per treatment group). The dose of tavapadon will be titrated and adjusted over the first 13 weeks of the trial and then maintained for 14 weeks. The planned duration of treatment is 27 weeks, including the Titration and Maintenance Phases. The investigational medicinal products (IMPs) will be taken orally.

The trial design is depicted in [Figure 1](#).

Figure 1: Trial Schematic

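### SAP 5.16.1 summarises plasma concentrations by visit only, whereas protocol 9.4.3 calls for dose and visit, and the SAP gives no reason for dropping dose

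*SAP*

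**What the plan says.** The protocol lists the pharmacokinetic endpoint in section 3, Table 3, as "Plasma concentrations of tavapadon and its metabolite (if required) at baseline (Day 1) and at Weeks 5, 11, 14, 22, and 27". Its analysis is in protocol 9.4.3, where concentrations of tavapadon and the major metabolite "will be summarized by dose, visit, and nominal time (if applicable". The same section gives exposure-response work to a separate PK analysis plan and adds that "Plasma concentrations will also be pooled with data from other trials in a population PK analysis", with those results reported outside the main clinical study report.

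SAP 5.16.1 has one sentence on how the concentrations are grouped: "Plasma concentrations of tavapadon and CV-0000053 (metabolite) will be summarized separately using descriptive statistics by visit". The mean plots are by nominal visit. SAP 5.16 names the analysis sets for listings, tables and figures and does not mention dose.

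On dosing, protocol 4.1.2 says: "The dose of tavapadon will be gradually titrated to 15 mg QD in all subjects over the first 14 weeks of the trial", unless intolerance prevents it. For the Maintenance Phase, "Subjects will receive the highest tolerated dose level that is achieved during the Dose Adjustment Phase", and no further adjustment is allowed.

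**The concern.** Once doses have diverged between subjects, a mean by visit averages over whatever doses happen to be in use. It describes the flexible-dose regimen as given, but a reader cannot recover from it the concentration seen at 5, 10 or 15 mg. The protocol promised that breakdown, and protocol 4.3 reports that exposure increased with dose over 5 to 15 mg, so the levels being pooled are expected to differ.

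What is at stake is limited. The endpoint in Table 3 is still delivered, since concentrations are reported at every listed visit. What is missing is a dose-specific level in the study report. A second, smaller issue is that the dose mix behind the mean can shift between Weeks 22 and 27 through dropout, even though no subject may change dose in that period.

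**Working it through.** There is no planned figure to reproduce. The check is a comparison of texts, followed by an illustration of size.

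**1. Grouping factors side by side.**

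| Source | Grouping of the concentration summary |
|---|---|
| Protocol 9.4.3 | dose, visit, nominal time where applicable |
| SAP 5.16.1, tables | visit |
| SAP 5.16.1, plots | nominal visit |

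The conditional wording in the protocol attaches to nominal time, not to dose. Nominal time matters little here because each visit has a single PK sample.

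**2. Could treatment group stand in for dose?** No. SAP 5.1 defines the groups as placebo and one tavapadon 5-15 mg arm, so a summary by arm does not separate dose levels.

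**3. Is dose restored or its omission explained elsewhere in the SAP?** I looked in the places where it could be:
- Sections 2 and 3.3 cover the endpoint and sample collection.
- Section 5.2 defines the PK Analysis Set without a dose grouping.
- Section 5.8 summarises average dose per phase and maximum tolerated dose, but on the FAS and not alongside the concentrations.
- Section 6 covers only later deviations from the SAP.
- Section 7, the revision history, has no entries.

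**4. Which visits are affected?**
- Day 1 is not, because no deviation from the early titration schedule is allowed.
- Weeks 5 and 11 cannot be judged, because the dosing table is redacted.
- Week 14 lies at the boundary of dose adjustment. Protocol 4.1.2 says that "Assessments will be conducted in the clinic at the end of Weeks 2, 5, 8, 11, 14, 18, 22, 26, and 27", and both it and SAP 1.4 put titration and adjustment in the first 14 weeks. SAP 1.1 says: "The dose of tavapadon will be titrated and adjusted over the first 13 weeks of the trial and then maintained for 14 weeks". These passages need reconciling in their own right. For the present point, the Week 14 sample need not reflect the maintenance dose.
- Weeks 22 and 27 fall in maintenance, where subjects stay on different doses.

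**5. Size of the pooling effect (illustration).** Assumptions: exposure proportional to dose over 5 to 15 mg, which protocol 4.3 does not claim, and assumed dose mixes, since the documents give none. With shares p5, p10 and p15, the pooled mean in dose units is 5·p5 + 10·p10 + 15·p15.

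| Mix 5/10/15 mg | Pooled mean | Relative to 5 mg | Relative to 15 mg |
|---|---|---|---|
| Equal thirds | (5 + 10 + 15)/3 = 10.00 | 2.00 | 0.67 |
| 20/20/60% | 1 + 2 + 9 = 12.00 | 2.40 | 0.80 |
| 5/5/90% | 0.25 + 0.5 + 13.5 = 14.25 | 2.85 | 0.95 |

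If exposure rises less than proportionally, all these ratios move towards 1.

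**6. Shift through dropout, Week 22 to Week 27 (illustration).** Spread the planned 27% dropout (protocol 9.2) evenly over 27 weeks, that is 1 percentage point per week. Then 78% remain at Week 22 and 73% at Week 27, about 144 and 134 of 184. The conditional loss is 0.05/0.78 = 6.41%. For the 20/20/60% mix:
- all lost from 15 mg: (12 − 0.0641 × 15)/0.9359 = 11.79, or −1.7%;
- all lost from 5 mg: (12 − 0.0641 × 5)/0.9359 = 12.48, or +4.0%;
- lost in proportion: no change.

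For equal thirds the extremes are −3.4% and +3.4%. Even the extreme cases are small.

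**The case against.** The best counter-argument is that a by-visit summary of a single flexible-dose arm is defensible on its merits. Dose is chosen by tolerability, so subjects at 5 or 10 mg are largely those who could not take more, and a by-dose mean compares self-selected groups. After Day 1 no post-dose sampling time is set and doses are taken at home, so any mean also mixes times since the last dose. Population PK handles both problems better and is already planned. The separate PK analysis plan may contain a by-dose table, and individual concentrations are in any case listed for the FAS.

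Much of this is fair as a limit on what a by-dose table can show, but it does not remove the discrepancy. Mixed sampling times affect the by-visit table just as much. Protocol 9.4.3 presents population PK as an addition, and it scopes the separate plan to exposure-response. Neither is said to replace the descriptive summary, and the SAP takes on that summary itself. The separate plan is not among the documents, so whether the trial will report dose-specific levels somewhere cannot be checked. The listings retain individual concentrations, but the SAP does not say that they show dose, and they are not a summary.

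It is also fair that the ratios above rest on assumed dose mixes and assumed proportionality. The finding does not depend on them.

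**Conclusion.** The concern holds as a minor point. The protocol names dose as a grouping factor for the concentration summary, the SAP omits it, and the SAP gives no explanation. This part rests on the two texts alone and is firm.

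The consequence is that by-visit means in the maintenance period, and possibly at Week 14, can pool different doses. On the stated assumptions the pooled mean could be two to nearly three times the 5 mg level and between two thirds and 95% of the 15 mg level. Drift through dropout between Weeks 22 and 27 is at most a few per cent. PK is not hypothesis-tested here, so type I error, power and the efficacy and safety conclusions are untouched.

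**What to change.** In SAP 5.16.1, summarise tavapadon and metabolite concentrations by dose at the time of sampling and by visit. The pooled by-visit summary can stay as an addition. If the sponsor prefers by-visit tables only, the SAP should state why it departs from protocol 9.4.3, or name the plan in which the by-dose summary will be reported. A by-dose plot is optional, since the protocol prescribes no PK plot.

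No new data are needed: protocol 8.6 records the dose amount with every PK sample. The SAP already uses dose elsewhere, in adverse events by dose at onset (5.15.1) and the analysis by final dose level (5.9.3.1). The cost is a wording change and a new table layout. The drawbacks are small cells at the less used doses and means that still mix times since the last dose; a footnote should say so, and should add that the dose groups are selected by tolerability.

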5.17. Protocol Deviations

All protocol deviations will be reviewed by the project team prior to database lock and unblinding to identify subjects with important protocol deviations. Summaries of important deviations will be presented by category of deviation. All protocol deviations will be presented in a listing by category along with a description and any additional comments.

6. CHANGES IN THE PLANNED ANALYSES

Should any deviations from the analyses specified in the authorized statistical analysis plan arise, such deviations will be documented in the final clinical study report.

7. REVISION HISTORY

Date	Revision	Rationale

9. APPENDICES

9.1. Interim Analysis Procedures

9.1.1. Description of Interim Analysis

Once approximately 67% (information fraction $t=2/3$) of the planned subjects (248 of 368 planned) have completed the study or discontinued, an interim analysis will be conducted to provide a sample size recalculation using the estimate of the nuisance parameter (standard deviation) in observed data of the primary efficacy endpoint, change from baseline to endpoint in daily “on” time without troublesome dyskinesia. Modifications to sample size will be based on the approach described in Section V.B of “Guidance for Industry: Adaptive Designs for Clinical Trials of Drugs and Biologics” (FDA, 2019), using the pooled sample variance calculated at the interim analysis. It should be noted that this is purely a check for nuisance parameter and no interim observed treatment difference will be part of the re-estimation. As mentioned in FDA guidance, as well as demonstrated by simulations results in [Section 9.1.2](#), this approach has no effect or very limited effect on type-I error rate. In addition, as the interim data will only be used to estimate nuisance parameter without any interim information of the treatment difference, the risk of operational bias that might otherwise present as the result of perceptions and conjectures on the treatment effect following sample size adjustment is minimized.

9.1.2. Operational Characteristics of the Interim Sample Size Re-estimation

9.1.2.1. Power Loss with Original Sample Size Under Circumstance of Increased Variability

The originally planned sample size depends on the assumption of the standard deviation of 2.5 hours in “daily on time without dyskinesia”. [Table 5](#) below illustrate the impact on the power of the study of a deviation from the assumption when an increased SD is observed in the study population. It is clear that the study may have substantially increased risk of not achieving its primary objective should this happen. Therefore, an interim sample size re-estimation with realistic SD assumption is important for the study.

Table 5: Impact of Standard Deviation Assumption on Statistical Power

Fixed Sample Size of N=368 (270 completers with 27% DC rate)		
	Type I error rate (α)	Power to detect $\Delta \geq 1$ hr vs Placebo
SD = 2.5 hr	0.049	90.4%
SD = 3.0 hr	0.049	77.6%
SD = 4.0 hr	0.049	53.1%

9.1.2.2. Sample Size Re-estimation Rule

The sample size re-estimation will follow the rule below.

$$N_F = \begin{cases} 368 & N_{new} < 368 \\ N_{new} & 368 \leq N_{new} \leq 528 \\ 528 & N_{new} > 528 \end{cases}$$

where 368 is the originally planned sample size, 528 is the maximum allowable sample size, and N_{new} is the total sample size (two treatment group combined) for 90% power to detect a difference of 1 hour “on time without dyskinesia per day” (as originally planned d_{plan}), at a two-sided alpha level of 0.049 calculated using pooled standard deviation at the IA.

$$N_{new} = \text{ceil} \left(\text{ceil} \left(\frac{4s_p^2 (z_{\alpha/2} + z_{\beta})^2}{d_{plan}^2} \right) \right) / .73$$

where

$d_{plan} = 1$ is the targeted difference in group means as originally planned

$\alpha=0.049$ is the nominal type 1 error rate for final analysis

$\beta=0.1$, i.e. $P(z>z_{\beta})=1-0.9$ for 90% power

s_p^2 is the pooled variance derived as

$$s_{pooled}^2 = \frac{(n_P - 1)s_P^2 + (n_T - 1)s_T^2}{n_P + n_T - 2}$$

n_P and n_T are the number of observations of placebo and tavapadon excluding missing values at the IA and s_P^2 and s_T^2 are the sample variance of placebo and tavapadon at the IA.

The factor of 0.73 is applied based on the expected dropout rate of 0.27.

9.1.2.3. Operating Characteristics Assessments

The impact of the sample re-estimation approach on the overall type I error rate and the statistical power were investigated using simulations. Data of 1,000,000 simulated trials for each of the two treatment groups were generated using random number generator following normal distribution under the null and the targeted alternative hypotheses with different standard deviations (Section 9.1.4). Table 6 below summarize the results from the simulation study. It confirms that the overall type I error rate is controlled below 0.05 level while the statistical power under the originally targeted alternative hypothesis is increased in cases where the assumption of SD is not realistic.

Table 6: Operating Characteristics of Sample Size Re-estimation Procedure

	Under Null Hypothesis where True $\Delta = 0$					Under Alternative Hypothesis of $\Delta = 1$					
	Overall Type I error rate (α)	Prob. of Final Size at 368	Prob. Final Size 369-527	Prob. Final Size 528	Mean Final Size	Power	Prob. of Final Size at 368	Prob. Final Size 369-527	Prob. Final Size 528	Mean Final Size	Bias of Point Estimate
SD = 2.5	0.0493	57.8%	42.2%	<0.1%	382	91.4%	57.8%	42.2%	<0.1%	382	0.00020
SD = 3.0	0.0495	0.1%	44.9%	55.0%	504	88.9%	0.1%	44.9%	55.0%	504	0.00016
SD = 4.0	0.0490	0%	0%	100%	528	68.7%	0%	0%	100%	528	0.00003

9.1.3. Conduct of the Interim Analysis

The interim analysis will be conducted by an independent IARC. The roles and responsibilities of the IARC members will be defined in the IARC charter.

Once the interim analysis time point is reached, the blinded statistical team will prepare a dataset containing the two key variables, a subject identifier and the change from baseline to endpoint (Week 26) in total daily “on” time without troublesome dyskinesia. Only subjects in the mITT population who have completed the study or discontinued will be included in this analysis. Missing data will not be imputed (i.e., only observed data will be included in the analysis). This dataset will be transferred via secured method to an independent unblinded statistical team outside the study personnel to apply treatment assignment information to the data and to calculate the pooled variance. This value then will be used to recalculate the final sample size (see [Section 9.1.2.2](#)) and be presented to the IARC. Based the outcome of the re-estimation, the IARC will make one of the following recommendations to Cerevel:

- Recommendation 1: If the re-calculated sample size N_F is >528 , the IARC will recommend increasing the sample size to 528, provided no known or identified safety issues at the time of interim analysis, to ensure adequate power at the final analysis.
- Recommendation 2: If the re-calculated sample size N_F is between 368 and 528 inclusively, the IARC will recommend increasing the sample size to N_F , provided no known or identified safety issues at the time of interim analysis, to ensure adequate power at the final analysis.
- Recommendation 3: If the re-calculated sample size N_F is less than 368, the IARC will recommend that the trial enrollment will continue to 368 as planned.

Strict firewall will be set in place for the interim analysis to guard the integrity of blinding. The blinded team will in no time have any access to treatment assignments and the unblinded independent statistical team, as well as the IARC, will in no time have access to the ongoing live clinical database and will keep the treatment assignment information in strict confidence.

